#### 4. GOAL AND OBJECTIVES

We propose to maintain patient safety while reducing the substantial VMMC follow-up workload burden by using two-way mobile phone texts to provide in-person review only for men who indicate a desire or need for follow-up. This tailored approach to post-procedure VMMC care could reduce unnecessary visits and remove barriers for VMMC clients without deterioration of quality care. I-TECH's diverse, expert team of researchers from the University of Washington, Seattle, USA; Aurum Institute's office in Johannesburg; and Medic Mobile, Nairobi, Kenya, will test this mHealth intervention. We believe that bi-directional, interactive, text-based short message service (SMS) during the most critical 14 days after circumcision will help men identify and act on any sign of an adverse event, thereby seeking in-person follow-up only when an AE is suspected and reducing unnecessary visits. Reduced in-person follow-up could also free healthcare workers to perform additional **VMMC** surgeries. Using a prospective, randomized control trial (RCT), our intervention compares two groups of clients with cell phones: 1) standard care (control group) and 2) clients who receive and respond to a daily text with in-person follow-up only if desired or if an AE is suspected (intervention). Both arms complete a study-specific, Day 14, in-person, follow-up review for verification of self-reports (intervention) and comparison (control). Our specific objectives are to:

Objective 1: Determine if 2-way texting can safely reduce VMMC follow-up visits

Approach: Un-blinded, prospective, non-inferiority, RCT in high-volume facilities providing VMMC. Two-way texting (**2wT**) will provide interactive, text-based follow-up. 2wT men healing without complication could decline in-person follow-up; those with suspected AEs will be referred to in-person care. We will compare the safety outcome of combined moderate or severe AE rate ≤ Day 14 post-VMMC and the workload outcome of average number of in-person follow-up visits between control and intervention arms.

Objective 2: Estimate the cost savings associated with 2wT over routine VMMC follow-up

Approach: We will determine the programmatic costs of 2wT from a systems perspective, including the technology , healthcare worker costs, and client perspective (travel, text costs, missed work). We will estimate the incremental

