#### RANDOMIZATION PROCESS:

We will conduct randomization using a randomized block design, ensuring that each group of 20 envelopes has 10 intervention and 10 control per block, shuffling each block to ensure a near random order. The full set of 1104 will be numbered before distribution to sites. Each group assignment envelope will be selected by the coordinator and then opened by the participant and shown to the coordinator or 2WT enrollment coordinator. Security envelopes will be used to help prevent selection of assigned group. Subjects within each block are randomly assigned to treatment conditions. This design reduces variability within treatment conditions and potential confounding, allowing for more interim analysis with near equal size groups and more certain randomization within sites.

Standard VMMC care (Control arm): For the 552 men randomized into the control arm, Aurum Institute follows all NDOH protocols based on WHO guidelines  including routine surgical VMMC follow-up on post-surgery days 2, 7 and 21 (Table 1) . Patients may seek care outside scheduled visits for suspicion of AEs at any healthcare facility at any time but most often return to their VMMC site. Referral cards for VMMC clients provide local numbers for patients to text, call, or request a call back for emergencies. A standardized approach is used to assess, identify, and record the severity of AEs . All VMMC care, from assessment of all AEs through complete healing, is provided free to clients from NDoH. Clients who do not return to the clinic for follow-up on Day 2 or Day 7 are traced: 3 attempts by phone and then 1 attempt at in-person tracking after which they are considered lost to follow-up (LTFU). There is no tracing for Day 21 visits. For the purposes of this study, control arm VMMC clients will be asked to come in on Day 14 for an additional follow-up visit. Active follow-up by phone call is provided at Day 14.

[figure not shown]

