VMMC care procedures (2wT arm): We will conduct a prospective, un-blinded, randomized control trial (RCT) among VMMC clients in a 1:1 ratio of control to intervention. Study participants and clinic staff are not masked to treatment. For the 552 men randomized into the intervention arm, men in the 2wT will receive routine VMMC surgical care and counseling, including referral cards for emergencies. 2wT clients will receive automated daily texts from days 1-14 (Table 1 and Figure 3). It is free to receive call and texts; it costs approximately R0.20 to send a SMS in RSA . If they respond that they suspect no adverse event, no immediate follow-up action will be taken. If a 2wT VMMC client responds affirmatively to any daily text that he

[figure not shown]
suspects an AE, a VMMC nurse will exchange modifiable, scripted texts with the client to determine the symptoms, frequency, and severity. Then, if deemed necessary, the client will be asked to return to clinic the following day or earlier if an emergency is suspected. AE management will adhere to NDOH standard care. If 2wT patients do not respond to texts on Day 2 or Day 7, the same NDOH tracing process will be activated on Day 14, after which they will be considered LTFU. All study participants will be asked to come to the clinic for study-specific, Day 14 follow-up to review healing and verify adverse event reporting. Day 14 was chosen for verification because 95% of all AEs within a similar VMMC program in Zimbabwe are reported Day 14 or earlier 61, suggesting that most AEs have occurred by this time point. In a previous field study of AEs, the most common AEs of bleeding and infection were found a mean of 6.7 and 9.0 days, respectively, after VMMC , further supporting the 14 day period used in this and a previous study. The Day 14 review will be conducted by routine VMMC providers according to NDOH review guidelines. At Day 21, we will implement a brief text-based survey with 2wT clients to ascertain complete healing, providing stronger inferences at study completion.

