#### 10. DATA ANALYSIS:

For Objective 1, the 2wT safety outcome of interest is cumulative AE rate (moderate or severe) ≤ Day 14. In RSA, and similar to other countries in the region. moderate AEs are those which include symptoms requiring modification of activity, but not resulting in loss of work or cancellation of social activities while severe AEs are those with incapacitating symptoms, requiring bed rest and loss of work 66. Incidence of AEs before Day 14 will be extracted from routine VMMC data for both 2wT and control. Incident AEs on Day 14 will be identified, classified, and graded for severity using routine NDOH protocols  and recorded on routine VMMC AE forms. We will compare cumulative rates of any moderate or severe AE ≤ Day 14 between groups using Fisher's exact test as the expected number of AEs is low. The rates will be calculated per arm as: (# moderate + severe AEs)/ (total # VMMC clients who attend/responded to 2, 7 or 14 Day follow-up visits or texts). Multivariate logistic regression models (any AE v none) will quantify the magnitude of difference, adjusting for any potential confounders. To determine follow-up visit reduction, we will compare the mean number of in-person visits for intervention and control using a t-test. A multivariate linear regression model will further quantify the effect of intervention on visit reduction, adjusting for potential confounders. Secondary outcomes include: AE rates on Day 14, texting response rate, time between 2wT AE text reporting and follow-up, severity of AEs. We will perform appropriate summaries of missing data and LTFU, testing for systematic differences in response by study arm. We hypothesize that 1) 2wT is non-inferior to routine follow-up for patient safety and that 2) 2wT will reduce unnecessary follow-up over standard care.

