**Expanding and Scaling Two-way Texting to Reduce Unnecessary Follow-Up and
Improve Adverse Event Identification Among Voluntary Medical Male
Circumcision Clients in the Republic of South Africa**

NCT04327271

[name], Principal Investigator

Statistical Analysis Plan (PDF/A) Version Date 8/26/19

Sample size and power:

RCT to determine no inferior AE ascertainment using 2-way texting rather than routine care. Randomization will be 1:1 between routine care and the texting intervention. If routine care AE ascertainment is 0.5% as evidenced from Aurum Institute program records, and 2-way texting increases AE ascertainment to 2.0% similar to our intervention arm AE ascertainment rate for the same intervention in our prior study in Zimbabwe (1.88%), and if we take -0.25% to be our noninferiority margin, and assume 10% LTFU, enrolling 1,104 men will give 80% power to establish noninferiority. In other words, 1,104 men (at least 994 of whom provide analyzable data) will provide at least 80% power to rule out a decrease of more than 0.25% based on the lower bound of the one-sided 95% confidence interval for the difference between arms in the proportion with AEs ascertained.

Sample sizes required to establish noninferior AE ascertainment using 2-way texting.

AE ascertainment		Sample size required for 80% power*		
Routine Care	2wText	N/group	Total N	+ 10% increase for LTFU
0.5%	1.50%	782	1564	1738
0.5%	2.00%	497	994	1104

* Calculated using Statistical Solutions Nquery Advisor version 8.4.1.0, two-group test of non-inferiority in proportions.

DATA ANALYSIS:

1. For the 2wT safety outcome of interest is cumulative AE rate (moderate or severe) \leq Day 14. In RSA, and similar to other countries in the region, moderate AEs are those which include symptoms requiring modification of activity, but not resulting in loss of work or cancellation of social activities while severe AEs are those with incapacitating symptoms, requiring bed rest and loss of work ¹. Incidence of AEs before Day 14 will be extracted from routine VMMC data for both 2wT and control. Incident AEs on Day 14 will be identified, classified, and graded for severity using routine NDOH protocols ² and recorded on routine VMMC AE forms.

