To test our noninferiority hypothesis, we will compare cumulative proportion (rate) of any moderate or severe AE ascertained \leq Day 14 between groups by comparing the lower limit of the one-sided 95% confidence interval of the difference in proportion between groups, to the noninferiority margin. The rates will be calculated per arm as: (# moderate + severe AEs)/(total # MC clients who attend 2, 7 or 14 Day follow-up visit). Based on our RCT in Zimbabwe, we may actually observe an increase in AEs; in that case, we will then seek to establish superiority of the two-way texting group by comparing arms with Fisher's exact test. While our study design provides limited power for this comparison (45%), there's no statistical impediment to performing both noninferiority and superiority comparisons in a noninferiority trial. To determine follow-up visit reduction, we will compare the mean number of in-person visits for intervention and control using a t-test. A multivariate linear regression model will further quantify the effect of intervention on visit reduction, adjusting for potential confounders. Secondary outcomes include: AE rates on Day 14, texting response rate, time between 2wT AE text reporting and follow-up, severity of AEs. We will perform appropriate summaries of missing data and LTFU, testing for systematic differences in response by study arm. We will examine individual mediating (e.g., referral follow-up, response rate) and moderating (urban/rural) variables ³. *We hypothesize that 1) 2wT is non-inferior to routine follow-up for patient safety and that 2) 2wT will reduce unnecessary follow-up over standard care.*

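### The protocol and the SAP give different denominators for the primary AE rate, so the rate is not uniquely defined and the non-inferiority verdict can depend on which is used

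*SAP*

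**What the plan says.** Protocol section 10 (Data Analysis, Objective 1) divides the number of moderate plus severe AEs by the "total # VMMC clients who attend/responded to 2, 7 or 14 Day follow-up visits or texts". SAP Data Analysis item 1 uses the same numerator but divides by the "total # MC clients who attend 2, 7 or 14 Day follow-up visit". Neither document gives an order of precedence.

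The SAP's sample size section describes the target as "the difference between arms in the proportion with AEs ascertained". Non-inferiority is shown if the lower limit of the one-sided 95% confidence interval (texting minus control) lies above -0.25 percentage points (pp). The section says to "assume 10% LTFU" and plans for 1,104 men, "at least 994 of whom provide analyzable data".

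Texting men have "in-person follow-up only if desired or if an AE is suspected" (protocol section 4). The one scheduled visit they share with control men is on Day 14: "All study participants will be asked to come to the clinic for study-specific, Day 14 follow-up" (protocol section 6).

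**The concern.** A texting man who replies that he has no problem and then misses Day 14 counts in the protocol's denominator and not, as a rule, in the SAP's. Such men exist only in the texting arm. In this trial a higher ascertained rate counts in favour of texting, so a smaller texting denominator pushes towards non-inferiority when the numerator is unchanged. With two written definitions in an unblinded trial, the choice could be made after the data are seen. The planned summaries of missing data would show unequal attendance but would not settle which rate is primary.

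The loss-to-follow-up allowance has the same gap. In the texting arm, tracing and loss to follow-up are triggered by not answering texts. A man who only texts is therefore not lost to follow-up, yet the SAP's rate leaves him out. It is unclear whether the 994 analysable men include him.

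**Working it through.** **The plan's own figure.** Inputs from the SAP: 0.5% control, 2.0% texting, margin 0.25 pp, one-sided 5%, 80% power.

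n per group = (1.645 + 0.842)² × [0.005 × 0.995 + 0.02 × 0.98] / (0.015 + 0.0025)² = 6.183 × 0.024575 / 0.00030625 = 496.1, so 497 per group and 994 in total. 994 / 0.9 = 1,104.4, stated as 1,104. The sample size reproduces; the problem is one of definition.

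**Which arm is affected.** Control men get no study texts, so attending and attending-or-texting pick out the same men. Control tracing is "3 attempts by phone and then 1 attempt at in-person tracking"; a phone contact alone puts a man in neither denominator. In the texting arm, attenders are a subset of attenders-or-responders.

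**Direction.**
- Numerator as written (all AEs counted): the SAP rate is equal to or above the protocol rate. For example, 10 AEs give 10/497 = 2.01% and 10/447 = 2.24%.
- Numerator limited to men in the denominator, as a proportion and Fisher's exact test imply: a man whose AE was found at an unscheduled visit and who missed Day 14 leaves both counts. If two of the ten are such men, 10/497 = 2.01% becomes 8/447 = 1.79%.

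**Can the verdict change?** Lower limit = d - 1.645 × √[pT(1-pT)/nT + pC(1-pC)/nC], compared with -0.25 pp. Control n is 497, the SAP's analysable number per group.
- 2 control, 5 texting, nT = 497: d = 1.006% - 0.402% = 0.604 pp, SE 0.530 pp, limit -0.268 pp (fails).
- Same AEs, nT = 470 (27 men only texted): d = 1.064% - 0.402% = 0.661 pp, SE 0.552 pp, limit -0.246 pp (passes).
- 4 control, 8 texting: -0.334 pp on 497 (fails), -0.229 pp on 442 (passes; 55 men only texted).

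**How often?** Simulation with 552 per arm and at least 1,000,000 trials per case. Assumptions: every man with an AE is counted; 90% of well control men attend (taken from the 10% allowance); 90% of well texting men attend or text. Share of trials in which the two denominators give different verdicts, by share of well texting men who attend:

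| True rates | 90% | 85% | 80% | 70% |
|---|---|---|---|---|
| 0.5% vs 2.0% | 0% | 1.6% | 3.3% | 6.0% |
| 0.5% vs 1.0% | 0% | 3.9% | 7.2% | 11.2% |

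Under these assumptions every disagreement is an SAP pass and a protocol fail, because all AEs are kept in the numerator. If instead 10% of texting men with an AE drop out of the SAP's numerator and denominator (80% attendance, 0.5% vs 2.0%), protocol-only passes (3.0%) exceed SAP-only passes (1.4%). With 5% dropped, the figures are 1.1% and 2.2%.

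**Power if all randomised men are the denominator.** Power = Φ[(pT - pC + 0.0025)/SE - 1.645], 552 per arm. At 0.5% vs 2.0%: SE = √(0.024575/552) = 0.00667, 0.0175/0.00667 - 1.645 = 0.978, power 83.6%. Men not seen count as no AE ascertained, so the rates may fall:
- both by a tenth (0.45% vs 1.8%): 81.1%;
- unequally: 78.1% (0.5% vs 1.8%) or 74.8% (0.45% vs 1.6%).

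**The case against.** The strongest reply is that only the SAP sets out a margin and a confidence-limit rule, and it states a denominator for that rule; the protocol plans Fisher's exact test and gives no margin. Reading the SAP as governing its own test is reasonable. An in-person denominator also fits the stated purpose of Day 14, which is to verify self-reports. This stands as a reason to keep the visit-only rate as a sensitivity analysis. It does not remove the conflict, because no text says that the SAP prevails. That statement covers only the text available: the protocol's sample size heading has nothing under it in this copy, and its appended procedures are not supplied.

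The size may also be small. All men are asked to attend on Day 14, willingness to attend is an inclusion criterion, and both arms receive an airtime credit. The worked examples lie near the margin: at the planning rates with 497 per arm, 2 vs 5 has a probability of about 1.0% and 4 vs 8 about 1.5%. Near the expected counts (2 vs 10 or 3 vs 10) the limit on 497 is +0.47 or +0.23 pp, a pass under either denominator. All of this stands and limits the size.

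A reader might infer that the SAP's denominator always favours texting. The documents do not support that: the direction is fixed only if all AEs stay in the numerator, and the numerator rule is itself unclear.

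**Conclusion.** The conflict is certain and concerns the primary safety rate, so it should be fixed. Its effect on the verdict is conditional. At the planning rates the two denominators disagree in 0% to 6.0% of trials as texting attendance runs from 90% to 70%; at 0.5% vs 1.0% the range is 0% to 11.2%. These figures rest on assumed attendance, which the documents do not give by arm, and on every man with an AE being counted.

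A reader might also infer that the visit-only rate is seriously biased against a count of all randomised men. At the planning control rate that is not shown. With a true 0.5% in both arms, 90% of well control men attending and 80% of well texting men, the spurious gap is 0.005/(0.005 + 0.995 × 0.80) - 0.005/(0.005 + 0.995 × 0.90) = 0.624% - 0.555% = +0.07 pp. It is -0.07 pp if the attendance figures are swapped. The point rests on the two definitions, not on a demonstrated bias.

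**What to change.** - State one primary definition in both documents. Numerator: men with at least one moderate or severe AE ascertained by Day 14 (men, not events). Denominator: all eligible randomised men who had surgical VMMC, with a man who has none recorded counted as none ascertained. This matches the SAP's own target.
- Keep the visit-or-text and the visit-only denominators as labelled sensitivity analyses, each with its numerator rule stated.
- Report exclusions, attendance at any visit and attendance at Day 14 by arm.
- Align the SAP's 994 analysable men with the definition and restate power as a range, 74.8% to 83.6% over the cases above. An assurance that the sample size is unaffected would not be justified, since power drops below 80% if the rates fall unequally.

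The cost is a few sentences in the two documents and no new data. The stated rates, and possibly the stated power, become slightly less favourable.

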#### RECRUITMENT SITES:

Study sites and population: In RSA, the World Bank estimated that there were 126 cellular subscriptions per 100 people in 2014 , indicating that the technology infrastructure exists and uptake is high. 2wT will be implemented in existing VMMC sites in Bojanala and Ekurhuleni Districts, districts purposefully selected for high VMMC volume static clinic locations and previous outreach success.

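### The main visit comparison leaves out site, although randomisation is meant to work within sites; if blocks stay whole at each site, its standard error is somewhat too wide

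*SAP*

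**What the plan says.** Three parts of the plan bear on this.

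- **Randomisation** (Protocol section 6, Randomization process). Envelopes are prepared in blocks, "ensuring that each group of 20 envelopes has 10 intervention and 10 control per block". The Protocol then says: "The full set of 1104 will be numbered before distribution to sites". Among the benefits it claims for the design are "near equal size groups and more certain randomization within sites". It does not call site a stratification factor, and it does not say that a block goes whole to a single site.
- **Sites** (Protocol section 5, Recruitment sites). "2wT will be implemented in existing VMMC sites in Bojanala and Ekurhuleni Districts". The number of sites is not given.
- **Visit analysis** (SAP, Data analysis, item 1; the same plan stands in Protocol section 10). First, "we will compare the mean number of in-person visits for intervention and control using a t-test". Then: "A multivariate linear regression model will further quantify the effect of intervention on visit reduction, adjusting for potential confounders". Neither document lists those covariates or mentions site as one. The SAP names urban versus rural setting, but only as a moderator to be examined.

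**The concern.** When allocation is balanced 1:1 inside each site, differences between sites in the mean number of visits cancel out of the comparison of arms. A pooled t-test still counts that between-site variation as noise, so it reports more uncertainty than the design leaves. The usual rule is that the analysis should reflect any factor by which randomisation was restricted.

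The documents give some reason to expect sites to differ. There are two districts, each site sets its own recruitment and screening methods, and Table 2 gives the location of the randomised stage as both rural and urban (although the study overview speaks of large urban clinics).

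At stake is the precision of the visit reduction, which is the workload outcome of Objective 1 and the second of the two stated hypotheses. There is also a pre-specification issue: an unnamed covariate list leaves the adjusted model to be chosen after the data are seen.

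**Working it through.** **The plan's own figure.** The only sample size in the documents is for the AE comparison, with 0.5% versus 2.0%, a margin of 0.25 percentage points, one-sided 5% and 80% power:

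n = (1.645 + 0.842)² × (0.005 × 0.995 + 0.02 × 0.98) / (0.02 − 0.005 + 0.0025)² = 6.183 × 0.024575 / 0.00030625 = 496.1, rounded up to 497 per group.

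This matches the SAP, and 994 / 0.9 = 1104.4 against the stated 1104. No sample size, SD or power is given for visits, so 497 per arm is used below as the analysable number.

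**Does the text fix the blocks to sites?** 1104 / 20 = 55.2, so the set is 55 full blocks plus 4 envelopes. If sites receive consecutive runs of numbers, most blocks stay whole. If envelopes are dealt out in another way, they may not. The text allows either.

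**Case A: whole blocks within sites.** Let ρ be the share of the within-arm variance in visits that lies between sites. It is not in the documents, so a range is assumed. The t-test standard error is proportional to 1, and the standard error under the design to √(1 − ρ). The ratio is therefore 1/√(1 − ρ):

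| ρ (assumed) | t-test SE too wide by |
|---|---|
| 0 | 0% |
| 0.01 | 0.5% |
| 0.02 | 1.0% |
| 0.05 | 2.6% |
| 0.10 | 5.4% |
| 0.20 | 11.8% |

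A simulation under the null (1,100 men, blocks of 20, 4 sites assumed, 3,000 runs, outcome SD 1, nominal 5%) checks the direction:

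| ρ | True SD of estimate | Mean t-test SE | Mean site-adjusted SE | Type I error, t-test | Type I error, adjusted |
|---|---|---|---|---|---|
| 0 | 0.0598 | 0.0603 | 0.0603 | 4.9% | 4.9% |
| 0.10 | 0.0559 | 0.0602 | 0.0572 | 3.2% | 4.2% |
| 0.20 | 0.0540 | 0.0602 | 0.0539 | 2.9% | 4.9% |

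The ratios of t-test to adjusted standard error, 0.0602 / 0.0572 = 1.052 and 0.0602 / 0.0539 = 1.117, agree with the formula. The simulated SD carries a relative error of about 1/√6000 = 1.3%, so the gap between 0.0559 and 0.0572 is within chance.

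**Case B: allocation unrelated to site.** At ρ = 0.20 the mean t-test standard error is 0.0603 against a true SD of 0.0603, so the t-test is valid. The site-adjusted standard error is 0.0540, so adjustment still gains precision.

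**Effect on conclusions** (497 per arm, two-sided 5% assumed).

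- The 95% half-width is 1.96 × √(2/497) = 0.124 SD. Multiplied by √(1 − ρ), it is 0.123 at ρ = 0.02, 0.118 at 0.10 and 0.111 at 0.20.
- At a standardised effect of 0.178, where the t-test has about 80% power, site-adjusted power is 81%, 82%, 84% and 88% for ρ of 0.02, 0.05, 0.10 and 0.20.
- From a standardised effect of 0.3 upward, power exceeds 99% either way.
- Table 2 schedules four visits for control (days 2, 7, 14 and 21) and one for 2wT (day 14). A count confined to 0 to 4 has an SD of at most 2, so 0.3 SD is at most 0.6 of a visit. Unscheduled visits could raise the SD, but the planned contrast is well above this size.

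**The case against.** The strongest reply is that nothing here is wrong as written. The Protocol never says randomisation is stratified by site, so a reader who takes the t-test standard error to be too wide as a plain fact goes beyond the text: that needs both whole blocks at each site and visit means that differ between sites, and neither is established. An unadjusted t-test followed by an adjusted regression is a common and valid sequence, and the regression may turn out to include site. Any error is on the safe side. The sample size was driven by the AE outcome alone, so precision gained on visits saves no participants.

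Most of this stands. It limits the point to a conditional one of small size. It does not remove the case for naming site, because the site-adjusted model is valid in both cases and at least as precise for practical purposes. That the regression could include site is a reason to say so before the data are seen.

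A reader might also infer that a wider standard error distorts the cost saving, since averted visits feed the costing. The documents do not support that. The costing (Protocol section 10, Objective 2; SAP item 3) is activity-based with a time-motion study and carries no standard error forward. With balance inside sites, the pooled and adjusted mean differences nearly coincide.

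**Conclusion.** The point holds conditionally and is minor. The design aims at randomisation within sites, but the main visit test ignores site and the follow-on regression does not name it. If blocks are kept whole within sites and visits differ by site, the t-test standard error is about 0.5% to 5% too wide for an assumed between-site share of 1% to 10%, and about 12% too wide at 20%. The documents supply no figure for that share, so the upper end should not be read as expected. The test is then conservative, with no excess of false positives. If allocation is unrelated to site, the t-test is valid and adjustment only adds precision.

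Given the large contrast in scheduled visits, the significance conclusion is unlikely to change. It would be tempting to extend the criticism to the AE outcome, but there the gain is negligible: at the planning rates about 497 × 0.005 = 2.5 and 497 × 0.02 = 9.9 events are expected per arm.

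**What to change.** In the SAP, Data analysis, item 1 (and Protocol section 10 to match):

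1. Make the main visit analysis a linear regression of visit count on arm, with site as a fixed effect and robust standard errors. Robust errors are suitable because the spread of visits will probably differ between arms.
2. Keep the t-test as a descriptive comparison.
3. In Protocol section 6, state whether each block of 20 goes whole to one site, and how the 4 envelopes beyond 55 full blocks are handled.

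No site-stratified AE analysis is needed on this account. The cost is a few sentences, with no new visits and no change in sample size. Site is not among the variables listed in Protocol section 11, but the trial must know it, because envelopes are issued to sites and men are enrolled there. The team should confirm that a site identifier is carried into the analysis file.
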